9.1 Site Monitoring Plan

Site monitoring is conducted to ensure the safety of human study participants and the protection of their rights and well-being. Monitoring also verifies that collected study data is accurate, complete and verifiable by source documentation and that the study is conducted in accordance with the protocol and operating procedures.

Monitoring for this study is the responsibility of the sponsor. The delegated monitor will evaluate study processes and documentation based on the approved protocol/amendment(s), Part C, Division 5 of the Food and Drug Regulations, the International Council for Harmonisation of Technical Requirements for Pharmaceuticals for Human Use (ICH), E6: Good Clinical Practice guidelines (GCP) and institutional policies.

The extent and nature of monitoring is outlined in the Monitoring Plan. The monitoring plan specifies the frequency of monitoring, monitoring procedures, the level of site monitoring activities (e.g., the percentage of participant data to be reviewed), and the distribution of monitoring reports. Monitoring activities will be performed both in person and remotely. Reports of findings identified during monitoring activities will be provided to sites detailing any required actions. Documentation of monitoring activities and findings will be provided to the site study team and the study QI. The institution and/or local REB reserves the right to conduct independent audits as necessary.

The Investigator is responsible for ensuring monitors and/or quality assurance reviewers are given access to all study-related documents noted above and study related facilities (e.g. pharmacy, diagnostic laboratory, etc.), and have adequate space to conduct the monitoring visit or audit.

9.2 Auditing and Inspecting

The investigator will provide direct access to source data/documents for the purposes of study-related monitoring, audits, and inspections by the REB, the sponsor, and applicable regulatory bodies. The investigator will permit the review of all study related documents (e.g. source documents, regulatory documents, data collection instruments, study data etc.) and will ensure access to applicable study-related facilities (e.g. pharmacy, diagnostic laboratory, etc.).

10 STATISTICAL CONSIDERATIONS

10.1 Study Hypotheses

Based on evidence from the transplant population, we hypothesize that patients who did not initially attain an initial robust immune response to two dose COVID-19 vaccination, a substantial proportion may attain improved humoral and cellular immunity against COVID-19 following a third vaccine booster with acceptable tolerability. We hypothesize that heterologous vaccination (e.g. a different vaccine from the first two doses) for the third dose may result in increased serologic response.

10.2 Sample Size Considerations

Approximately 500 patients with chronic kidney disease are presently enrolled in the study entitled “Determining the Safety and Efficacy of COVID-19 Vaccination in the Chronic Kidney Disease Population”, but this number is rapidly increasing. We have limited information to guide our sample size, but in the case series published in transplant patients 25% of patient who were seronegative responded to a booster vaccine, while 100% of those with “low positive” antibody levels responded to a booster vaccine. Similarly in a study from France the prevalence of positive SARS-CoV-2 antibodies increased 28% after the third dose.

Our sample size is based on serologic response for Anti-RBD as this measure may be a better correlate with neutralizing antibodies than Anti-Spike.^{22,23} In our pilot study we found that 60% of patients had attained convalescent serum levels of Anti-RBD by two weeks after post-second dose and therefore we expect no issues with finding eligible participants. For our sample size calculation, to achieve 80% power to detect 25% difference in individuals reaching convalescent serum levels of Anti-RBD receiving a COVID-19 from *mRNA-1273* versus

BTN162b2 at a two sided alpha of 0.05 assuming 25% response in the *BNT162b2* group based on the limited studies to date, we would require 58 participants in each study group. The 25% difference was determined by consensus by the Principal Investigators to represent a clinically important difference. Given the stratification by baseline vaccination received, there will be four study groups, requiring a sample size of 232 participants as shown in Table 2. A Bonferroni adjustment for the alpha will not be used. A similar sample size calculation is obtained if the nested (two) chi-squared tests for the primary outcome of this study are considered the equivalent of a logistic regression equation with the baseline initial vaccine received as the two covariates. Assuming approximately 25% response to a booster dose, and the general rule that 10 outcome events are required per covariate, and 10% drop out during the one month period of the primary outcome, a total sample size of 89 would be required. Capacity to enroll is higher, therefore the target sample size will be 300 participants to avoid under-powering the study, and will account for up to 10% participant loss to follow-up due to death or new COVID-19 infection during the 1 month follow-up period for the primary outcome.

Table 2: Potential sample size calculations based upon differences in Anti-RBD response observed between BNT162b2 and mRNA-1273 vaccines at a Power (1- β) of 80% and α 0.05

Clinically Significant Difference	BNT162b2 Response ^a	mRNA-1273 Response ^a	Power (1- β)	Alpha (α)	Required Sample Size	Required Total Sample Size (4 Groups)
30%	25%	55%	80%	0.05	41	164
30%	50%	80%	80%	0.05	39	156
30%	65%	95%	80%	0.05	27	108
25%	25%	50%	80%	0.05	58	232
25%	50%	75%	80%	0.05	58	232
25%	65%	90%	80%	0.05	43	172
20%	25%	45%	80%	0.05	82	328
20%	50%	70%	80%	0.05	93	372
20%	65%	85%	80%	0.05	73	292
15%	25%	40%	80%	0.05	152	608
15%	50%	65%	80%	0.05	170	680
15%	65%	80%	80%	0.05	138	552

^aDefined as reaching median convalescent serum levels of anti-RBD.

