AE	Adverse Event/Adverse Experience
AEFI	Adverse Event Following Immunization
Anti-NP	Anti- nucleocapsid Protein
CC	Coordinating Centre
CIOMS	Council for international Organizations of Medical Sciences
CRF	Case Report Form
CTCAE	Common Terminology Criteria for Adverse Events
CTO	Clinical Trial Ontario
CCTS	Centre for Clinical Trial Support
CKD	Chronic Kidney Disease
COVID-19	Coronavirus 19
EC	Ethics Committee
ELISA	Enzyme Linked Immunosorbent Assay
HD	Hemodialysis
IB	Investigator's Brochure
ICH	International Council for Harmonisation of Technical Requirements for Pharmaceuticals for Human Use
IP	Investigational Product
DSMB	Data Safety Monitoring Committee
DSPC	1,2-distearoyl-sn-glycero-3-phosphocholine
eCRF	Electronic Case Report Form
pCRF	Paper Case Report Form
EDC	Electronic Data Capture

GCP	Good Clinical Practice
ICF	Informed Consent Form
MedDRA	Medical Dictionary for Regulatory Authorities
ORN	Ontario Renal Network
PD	Peritoneal Dialysis
PHI	Personal Health Information
PHIPA	Personal Health Information Protection Act
PI	Principal Investigator
PM	Product Monograph
QI	Qualified Investigator
RBD	Receptor-Binding Domain
REB	Research Ethics Board
RCT	Randomized Controlled Trial
SAE	Serious Adverse Event/Serious Adverse Experience
SC	Steering Committee
snELISA	Surrogate neutralization ELISA
SOP	Standard Operating Procedure
SRI	Sunnybrook Research Institute
SUADR	Serious and Unexpected Adverse Drug Reaction
TMF	Trial Master File
TDL	Task Delegation Log
USP	United States Pharmacopeia

Protocol Summary

Full Title	BOOST KIDNEY: A Multi-Centre 12 Month Parallel-Group Randomized Control Trial of BNT162b2 versus mRNA-1273 COVID-19 Vaccine Boosters in Chronic Kidney Disease and Dialysis Patients with Poor Humoral Response following COVID-19 Vaccination
Short Title	BOOST KIDNEY
Phase	II/III
Protocol Number	3750
Version Date	Version 5.0, Nov 5, 2021
Study Duration	1 year
Principal Investigator	[name]
Setting	Multicenter, 5 Dialysis Centres in Ontario and British Columbia, Canada
Number of Participants	300 participants
Study Design	Four arm parallel randomized controlled trial of BNT162b2 versus mRNA-1273, third dose of the COVID-19 vaccine stratified by initial two dose vaccine type
Main Inclusion Criteria	Dialysis and non-dialysis chronic kidney disease (Stage 3b-5)
Primary Outcome(s)	Evaluate effect of third dose COVID-19 vaccine booster (BNT162b2 versus mRNA-1273) on serologic SARS-CoV-2 response (Anti-RBD) at 1 month following booster dose.

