Secondary Outcome(s)	
 1. Evaluate effect of third dose COVID-19 vaccine booster (BNT162b2 versus mRNA-1273) on Anti-Spike and SARS-CoV-2 viral neutralization at 1 month following booster dose. 2. Anti-Spike and Anti-RBD response at study enrolment, 3 months, 6 months and 12 months following booster dose. 3. Flow cytometry on PBMC, single-cell RNA sequencing and ELISPOT prior to, 1 month, and 6 months following booster dose to evaluate SARS-CoV-2 specific B and T-Cell response. 4. Evaluate adverse effects related to third dose of vaccine through a questionnaire 48 hours -14 days, and 30 days following third vaccine dose. 5. Differences in COVID-19 infections, symptomatic COVID-19 infections, hospitalization, and death between study groups.
Statistical Analysis	
Intention to treat analysis for the primary outcome with two Chi-Squared test or Fisher's exact test for the primary outcome. Non-parametric testing for differences in antibody level between study groups. Mixed effects models will be used for comparison of longitudinal antibody levels.

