5.5.1 Randomization Procedures

Stratified randomization will be performed centrally upon study enrolment with 1:1 receiving *BNT162b2* mRNA COVID-19 Vaccine (*COMIRNATY®/Pfizer-BioNTech*), and *mRNA-1273* SARS-CoV-2 Vaccine (*SPIKEVAX®/Moderna*) with stratification by baseline vaccine type *BNT162b2* or *mRNA-1273* given possible differences in vaccine immunogenicity in this population and heterologous priming.

The Participant whose written informed or preliminary verbal consent was obtained and eligible for the study will be randomized. Allocation will occur through identical, sequentially numbered, opaque, sealed envelopes. The two interventions will be the two COVID-19 vaccines which have been used predominantly in the dialysis population: the *BNT162b2* mRNA COVID-19 Vaccine (*COMIRNATY®/Pfizer-BioNTech*) and *mRNA-1273* SARS-CoV-2 Vaccine (*SPIKEVAX®/Moderna*). The *BNT162b2* mRNA Covid-19 Vaccine (*COMIRNATY®/Pfizer-BioNTech*), is administered in 30 µg per dose while the *mRNA-1273* SARS-CoV-2 Vaccine (*SPIKEVAX®/Moderna*) is administered as 100 µg. Vaccines will be released from participating hospital pharmacies. Approval has been granted by the respective government agencies in Ontario and British Columbia.

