10.5.1 Statistical Analysis of the Primary Outcome

An intention-to-treat analysis will be followed for the primary outcome. The primary outcome will be the proportion of patients who attain convalescent serum levels of Anti-RBD at 1 month (30 days) following third dose of vaccine. Two Chi-Squared test or Fisher's exact test will be used, one for those who received first two doses of *BNT162b2* and the second for those who received *mRNA-1273* for the first two doses. This study is powered to determine differences between the use of *mRNA-1273* vaccine and *BNT162b2* vaccine as the booster dose on the primary outcome based on a clinically significant difference of 25% as described above in the sample size considerations. An adjusted analysis with logistic regression modelling will be performed if imbalance in baseline characteristics is found to between study groups following stratified randomization. Individuals who develop new COVID-19 infection as determined by a positive Anti-NP serologic test or positive SARS-CoV-2 RT-PCR nasopharyngeal swab during the study will be excluded from analysis of the primary outcome.

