13.3.1 Benefits

Benefits to participants include the potential for increased immunity following a booster dose of vaccine. Results from this study will provide evidence to help determine whether a booster vaccination may be beneficial in this patient population, if a specific vaccine is more beneficial for boosting, and may inform policy change at the provincial and/or national level for patients with chronic kidney disease.

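### Do two unadjusted primary tests, one per initial-vaccine stratum and with no rule for a split result, undermine the stated 0.05 and 80%?

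*Combined protocol and SAP*

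**What the plan says.** The Protocol Summary gives the primary outcome as one comparison: "Evaluate effect of third dose COVID-19 vaccine booster (BNT162b2 versus mRNA-1273) on serologic SARS-CoV-2 response". Its statistical line already announces two tests: "Intention to treat analysis for the primary outcome with two Chi-Squared test or" Fisher's exact test. Section 10.5.1 explains the two: a chi-squared or Fisher's "exact test will be used, one for those who received first two doses of" BNT162b2, and a second for those primed with mRNA-1273. The same section says the study is powered to compare mRNA-1273 with the BNT162b2 "vaccine as the booster dose on the primary outcome based on a clinically significant difference of 25" percentage points.

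Section 10.2 assumes 25% versus 50% reaching the convalescent anti-RBD level, two-sided 0.05 and 80% power. It obtains 58 per group and multiplies by four groups to get 232. It adds: "A Bonferroni adjustment for the alpha will not be used". The target is 300, allowing for up to 10% loss before the one-month outcome. Randomisation is 1:1 within each initial-vaccine stratum (5.5.1, 6.1.2). No expected split between the strata is given.

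**The concern.** One stated aim is served by two primary tests, each at the full 0.05, and multiplicity adjustment is declined without a reason. If the two strata disagree, the plan does not say whether a booster difference has been shown. Section 13.3.1 suggests that an overall answer is wanted, since it says results may show "if a specific vaccine is more beneficial for boosting, and may inform policy change at the provincial and/or national level". A conclusion drawn from whichever stratum turned out positive would have an error rate above the stated 5%. A conclusion that needed both strata would have less than the stated power.

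A second worry is stratum size. Four groups of 58 need 116 evaluable patients in each stratum, but 1:1 allocation inside a stratum does nothing to fix how large that stratum is. If most recruits had received the same initial vaccine, the other test could be badly underpowered even with 300 enrolled.

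**Working it through.** **Inputs.** Response 25% and 50%, two-sided 0.05, power 80%, four groups, target 300 and loss up to 10% (all 10.2); two tests, one per stratum (10.5.1).

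**The plan's own figure.** Pooled two-proportion formula with mean rate 0.375:

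n = [1.960 × √(2 × 0.375 × 0.625) + 0.842 × √(0.25 × 0.75 + 0.50 × 0.50)]² / 0.25² = [1.960 × 0.6847 + 0.842 × 0.6614]² / 0.0625 = 57.67, so 58 per group, and 4 × 58 = 232. Both match. One overall comparison at these rates would need only 2 × 58 = 116 in total, so the plan sized two tests.

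**What each reading implies.** The strata share no patients, so the tests are independent. Evaluable patients at target: 300 × 0.9 = 270, or 67.5 per group with equal strata. Chi-squared power is 80.2% at 58 per group and 85.9% at 67.5.

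- Either test suffices, both nulls true: 1 − 0.95² = 9.75% nominal. Fisher's test is conservative. Its exact size for common rates of 25–50% is 3.05–3.24% at 58 per group, giving 6.0–6.4% overall.
- Both tests required: 0.802² = 64% at 58 per group; 0.859² = 74% at 67.5.
- Separate questions: 5% and at least 80% per test, as stated.

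**Which reading the design fits.** Section 2.3 lists four arms by initial vaccine and booster. Section 5.5.1 stratifies "given possible differences in vaccine immunogenicity in this population and heterologous priming". Section 10.1 hypothesises that a different vaccine "for the third dose may result in increased serologic response". That favours mRNA-1273 after BNT162b2, and BNT162b2 after mRNA-1273. With equal strata and opposite 25-point effects, a pooled difference would be (+25 − 25)/2 = 0. Stratum-specific tests suit that hypothesis; a single overall claim does not.

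**What an adjustment would cost.** Under the Holm procedure at 67.5 per group, power at 0.025 is 78.4%. If both strata have the planned effect, power per stratum is 0.784 + (0.859 − 0.784) × 0.784 = 84%. If only one does, it is 0.784 + (0.859 − 0.784) × 0.025 = 79%, below the plan's 80%.

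**Stratum size.** Group size in the smaller stratum is 270 × share / 2. The shares are assumptions, because the documents give none.

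| Smaller stratum's share | Per group | Power (chi-squared) |
|---|---|---|
| 50% | 67.5 | 86% |
| 45% | 60.75 | 82% |
| 43% | 58.05 | 80% |
| 40% | 54 | 77% |
| 30% | 40.5 | 65% |
| 20% | 27 | 47% |

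The threshold is 116/270 = 43%.

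**Choice of test.** At 25% versus 50%, Fisher's exact power is 74% at 58 per group and about 82% at 67–68. At 58 per group the smallest expected cell is 58 × 0.375 = 21.75, so there is no sparse-data reason to prefer Fisher.

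**Two slips in 10.2.** The formula reproduces 11 of the 12 rows of Table 2. The 25% versus 45% row gives 88.09, so 89 and 356, not 82 and 328. The alternative total of 89 is 2 × 10 / 0.25 = 80, then 80/0.9. It is an events-per-covariate count, and calling it similar to 232 is loose. Neither figure sets the target.

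**The case for a change.** The strongest case for a change is that the Protocol Summary and 10.5.1 describe one booster comparison, while the heterologous hypothesis itself makes a split result foreseeable. A rule written before results would cost a sentence or two and no new data. Section 10.5 leaves the final analysis plan to be developed and 5.5.2 blinds the analysts, but neither supplies the rule. Unequal strata are also plausible: the pilot in 2.2 reported on BNT162b2 recipients, and 4.1 gives recruitment priority to patients from its successor study.

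Part of this stands. No rule is written, the single-question reading is not excluded, and stratum size is neither predicted nor controlled. The error-rate and power failures, however, arise only under the reading that fits the design less well. The multiplicity choice is open and prespecified, and replacing it with Holm would trade power for a guarantee that two separate questions do not need. A sentence declaring the strata separate, or a forecast of their sizes, would alter no test, no threshold and no target, yet would still need an amendment with ethics-board approval (13.2). The uneven shares in the table show sensitivity, not a shortfall found in the documents.

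**Conclusion.** No change follows. Taken as two stratum-specific questions, the primary analysis is sound: each test has 5% nominal error. With chi-squared, power for 25% versus 50% is 80% at 58 per group and 86% if 270 evaluable patients split evenly. Raising the target from 232 to 300 absorbs the 10% loss and tolerates a smaller stratum down to 43%. With equal strata it also keeps Fisher's test above 80%.

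The missing rule for a split result is a gap that analysts fill by reporting each stratum's result as its own, which is how 10.5.1 sets up the tests. An overall booster claim resting on one positive stratum would go beyond the planned analysis, and a reader could see that. The Table 2 row and the remark about 89 are clerical and do not affect the target.

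This rests on the separate-questions reading and on strata that are not far from equal. The documents support the first better than the alternative and are silent on the second.

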10.3 Planned Analyses

The primary outcome will be evaluated at 30 days (1 month) following the study intervention.

Subsequent analyzes will be planned at other time points in the study (3 months, 6 months, and 12 months) following study intervention.

10.3.1 Safety Review

Adverse event questionnaires completed following the study intervention will be reviewed continuously with planned safety reviews at 30 days by the Data Safety Monitoring Board.

10.4 Stopping Rules

This study will be stopped prior to its completion if: (1) the intervention is associated with adverse events that call into question the safety of the intervention; (2) difficulty in study recruitment or retention will significantly impact the ability to evaluate the study endpoints; (3) any new information becomes available during the trial that necessitates stopping the trial; or (4) other situations occur that might warrant stopping the trial.

10.5 Final Analysis Plan

The final analysis plan will be developed by the biostatistician in conjunction with the Principal Investigator. The targeted sample size for this study will be 300 due to feasibility, although a lower number are estimated to be required based upon sample size calculations above, and the final sample size may be adjusted by the Principal Investigator dependent upon study recruitment. If the final sample size is adjusted, a Clinical Trial Amendment will be filed. The proportion of patients receiving BNT162b2 and mRNA-1273 will be reported.

Quantitative Anti-SARS-CoV-2 IgG targeting the spike protein, RBD, nucleocapsid, and neutralizing antibodies will be reported at each time point as relative levels. Descriptive statistics will be used to describe baseline characteristics of patients in all four arms of the study. Mean

and median timing between first, second, and third (booster) vaccine dosage will be reported. Differences in the cell-mediated immunity as measured through flow cytometry on PBMC will be exploratory. Pre-specified clinical outcomes will include COVID-19 infections, COVID-19 related hospitalizations, and death.

10.5.1 Statistical Analysis of the Primary Outcome

An intention-to-treat analysis will be followed for the primary outcome. The primary outcome will be the proportion of patients who attain convalescent serum levels of Anti-RBD at 1 month (30 days) following third dose of vaccine. Two Chi-Squared test or Fisher's exact test will be used, one for those who received first two doses of *BNT162b2* and the second for those who received *mRNA-1273* for the first two doses. This study is powered to determine differences between the use of *mRNA-1273* vaccine and *BNT162b2* vaccine as the booster dose on the primary outcome based on a clinically significant difference of 25% as described above in the sample size considerations. An adjusted analysis with logistic regression modelling will be performed if imbalance in baseline characteristics is found to between study groups following stratified randomization. Individuals who develop new COVID-19 infection as determined by a positive Anti-NP serologic test or positive SARS-CoV-2 RT-PCR nasopharyngeal swab during the study will be excluded from analysis of the primary outcome.

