6.1.3.1 Identification of Individuals with Suboptimal Humoral Response

Patients enrolled in the pilot study “Determining the Safety and Efficacy of COVID-19 Vaccination in the Chronic Kidney Disease Population” (with Protocol CTO number 3604) or who are interested in the study who are found to have poor humoral response will be determined to be eligible for the trial by assessing their most recent antibody levels drawn at a minimum 1 month following their second dose of COVID-19 vaccine. Upon study enrolment SARS-CoV-2 antibodies against anti-Spike, anti-RBD, and anti-NP will be performed to exclude evidence of recent COVID-19 infection and confirm anti-RBD levels below convalescent serum levels.

Antibodies targeting the full-length spike protein (anti-spike) and its Receptor Binding Domain (anti-RBD) measured humoral response to SARS-CoV-2 vaccination and/or natural infection while antibodies to the nucleocapsid protein (anti-NP) detected natural SARS-CoV-2

infection, as this antigen is not targeted by the BNT162b2 vaccine. Antibody levels are reported as relative ratios to a synthetic standard included as a calibration curve on each assay plate.

Thresholds for positivity (seroconversion) were determined by aggregating data from negative controls and calculating the mean + 3 standard deviations. The median level of convalescent serum is determined by comparison to the median levels of convalescent serum taken 21-115 days post symptom onset in patients with COVID 19. The convalescent serum patients (n=211) were obtained from the Toronto Invasive Bacterial Diseases Network (REB studies #20-044 Unity Health, #02-0118-U/05-0016-C, Mount Sinai Hospital). had a median age of 59 years, 115/211 (55%) were male and included patients with mild (defined as not requiring hospitalization), moderate, and severe disease severity.

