7 STUDY SCHEDULE AND PROCEDURES

7.1 Study Procedure

Participants who meet study eligibility criteria and consent to participate will be enrolled in the study. At study enrolment baseline, serum will be collected for SARS-CoV-2 serology, neutralizing antibodies and in a subset determined by the Investigator, PBMC will be collected for assessment of cellular immunity at Sunnybrook Health Sciences Centre or University Health Network prior to receiving the booster dose. Patients who are already participating in the study “Determining the Safety and Efficacy of COVID-19 Vaccination in the Chronic Kidney Disease Population” (CTO Protocol Number 3604) and have been found to have poor humoral response to COVID-19 vaccination will be prioritized for recruitment. However, if a booster dose of COVID-19 vaccine is approved for subsets of the study population or the study population at large during the study period, patients remain eligible for randomization without serological confirmation of low antibody titres.

Vaccine will be administered by an individual trained in vaccine administration at the site.

Following vaccination, participants will be asked about adverse symptoms related to COVID-19 vaccination through a questionnaire at 48 hours -14 days either in person in the dialysis unit or by telephone and at 1 month post third dose.

Following the intervention with either third dose of booster vaccine, the participant will have blood collection for Anti-SARS-CoV-2 IgG antibodies targeting the full length spike protein, RBD, nucleocapsid protein at 1 month, 3 months, 6 months, and 12 months following receipt of the booster dose. For feasibility, neutralizing antibodies will only be performed at 1 month following third dose. Non-dialysis participants may have bloodwork testing as part of routine

clinical care at each time point to determine if the booster vaccine dose has impacted kidney function including a serum creatinine and a spot urine micro-albumin creatinine ratio.

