7.4 Baseline Data Collection

The Ontario Renal Reporting System (ORRS) and British Columbia's PROMISE databases will be used to obtain demographic information on all participants enrolled in the study. The Ontario Renal Network has already mandated provincial data collection regarding symptoms/adverse events related to vaccination and COVID-19 infection confirmed by SARS-CoV-2 RT-PCR in hemodialysis and peritoneal dialysis patients. Specifically the following variables will be collected in all participants: age, sex, prior COVID-19 (NP Swab), vascular access, cause of kidney disease, current immunosuppressive medications (defined as taking any of the following: antimetabolite agent, calcineurin inhibitor, cytotoxic medications, rituximab in prior 6 months, tumor necrosis factor alpha monoclonal antibodies, or glucocorticoids greater than prednisone 5 mg daily), autoimmune disease, diabetes mellitus, cancer, coronary artery disease, congestive heart failure, chronic obstructive lung disease, hypertension, obesity, hepatitis B non-responder status (defined as <10mIU/mL), and ABO blood type. In non-dialysis patients serum creatinine and proteinuria will be recorded.

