10.5.2 Statistical Analysis of Secondary Outcomes

Secondary outcomes will include the proportion of patients who attain Anti-Spike median convalescent serum at 1 month (30 days) following third dose of vaccine. Differences in relative antibody levels (Anti-Spike and Anti-RBD) and neutralizing antibodies between study groups will be assessed through the Mann-Whitney test. The relative levels of antibodies will be tracked

longitudinally for each patient permitting analysis of SARS-CoV-2 antibody kinetics following vaccination and will be assessed through a mixed-effects repeated measures model with random intercepts and fixed covariates following log transformation of relative ratios, which will be exploratory. Differences in serial levels in relative antibody levels will be compared through a mixed effects model as above. Similar to the primary outcome, those with a new positive Anti-NP serologic test or COVID-19 nasopharyngeal swab during the study will be excluded from analysis. An intention to treat analysis will be followed, although an exploratory per protocol analysis may also be reported.

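### The primary tests and titre comparisons do not adjust for enrolment anti-RBD, and the only adjusted primary analysis hangs on an undefined imbalance trigger with unnamed covariates

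*Combined protocol and SAP*

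**What the plan says.** The Protocol Summary gives "Intention to treat analysis for the primary outcome with two Chi-Squared test" or Fisher's exact test. Section 10.5.1 repeats this, with one test for each prior-vaccine stratum and no covariate. Logistic regression enters conditionally: "An adjusted analysis with logistic regression modelling will be performed if imbalance in baseline characteristics is found". No threshold, test or covariate list follows.

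For titres, section 10.5.2 says: "Differences in relative antibody levels (Anti-Spike and Anti-RBD) and neutralizing antibodies between study groups will be assessed through the Mann-Whitney test". No baseline term is mentioned. The only other model there is a repeated-measures mixed model with "random intercepts and fixed covariates following log transformation of relative ratios, which will be exploratory"; those covariates are not named either.

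Enrolment anti-RBD is scheduled for everyone. Section 6.1.3.1 states "Upon study enrolment SARS-CoV-2 antibodies against anti-Spike, anti-RBD, and anti-NP will be performed", section 7.1 states "At study enrolment baseline, serum will be collected for SARS-CoV-2 serology", and Table 1 marks the antibody sample at Study Enrolment. The list of baseline data in section 7.4 begins "Specifically the following variables will be collected in all participants: age, sex, prior COVID-19 (NP Swab), vascular access, cause of kidney disease" and runs to 16 items for all participants. No antibody level is among them.

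Section 10.2 sizes the trial at 58 per group and also remarks that "the nested (two) chi-squared tests for the primary outcome of this study are considered the equivalent of a logistic regression equation". That model carries the initial vaccine, not anti-RBD, and serves only the sample size. Section 10.5 leaves the final analysis plan still to be developed.

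**The concern.** The baseline value of the endpoint is usually among its best predictors, and the protocol itself treats baseline serology as informative. Section 10.2 cites booster response of 25% in seronegative and 100% in low-positive transplant recipients (a series of 24 and 6 patients, section 2.3), and section 10.5.3 forms subgroups by serologic history. Leaving this value out of the comparisons gives up precision that needs no extra blood draw.

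The trigger is a separate problem. Under randomization any baseline imbalance is due to chance, so whether an adjusted analysis exists would depend on a definition that could be settled after data are seen. Because enrolment titre is not in the section 7.4 list, the trigger could also be met, and a model fitted, without the covariate most likely to matter.

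**Working it through.** **1. The plan's own figures.** Inputs from section 10.2: 25% v 50%, two-sided alpha 0.05, power 80%.

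n = [1.96·√(2·0.375·0.625) + 0.8416·√(0.25·0.75 + 0.5·0.5)]² / 0.25² = (1.342 + 0.557)² / 0.0625 = 57.7, so 58 per group and 4 × 58 = 232. This matches the plan. Exact chi-squared power is 79.9% at 58 per group. With 300 enrolled and 10% lost, 300 × 0.9 / 4 = 67.5. Taking 67 per group (equal strata assumed), exact power is 85.7%.

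**2. How often chance alone meets the trigger.** Per stratum, 58 per group, the 16 variables of section 7.4; the definitions of imbalance are assumptions, since the plan gives none.

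- One designated variable at p<0.05: 5%.
- Any of 16 at p<0.05, independent: 1 − 0.95^16 = 56%. With pairwise correlation 0.5 (assumed): 37%.
- Any standardized difference above 0.2: for one variable z = 0.2/√(2/58) = 1.077, p = 0.281. For any of 16, 1 − 0.719^16 = 99.5% (96% at correlation 0.5).
- Any standardized difference above 0.1: about 100%.

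A 0.2 rule flags 16 × 0.281 = 4.5 variables on average. Section 10.2 uses a rule of 10 events per covariate. At 25% v 50%, a stratum has 14.5 + 29 = 43.5 events, enough for about four terms including booster. A two-term model meets the rule even at 25% in both arms (0.25 × 116 = 29 events).

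**3. What adjustment would gain.** The correlation (rho) between enrolment and 1-month log titre is not in the documents, so 0.3, 0.5 and 0.7 before truncation are assumed. The simulation uses normal log titres, a threshold set to give 25% v 50%, and 1:1 allocation within one stratum. It compares Pearson chi-squared with a likelihood-ratio test adjusted for baseline. Low-titre enrolment is represented by the lower 40% or lower 59% of baseline values, because 60% (section 10.2) or 41% (section 2.2) reached the convalescent level. Sections 4.1 and 7.1 allow serologic screening to be waived, which corresponds to no truncation. Replicates: 12,000 at 58 per group, 8,000 at 67. Cells show unadjusted → adjusted power, %.

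| Setting | rho 0.3 | rho 0.5 | rho 0.7 |
|---|---|---|---|
| 58/group, lower 40% | 79.4 → 81.0 | 80.0 → 82.7 | 80.0 → 85.3 |
| 58/group, lower 59% | 79.9 → 81.7 | 79.6 → 83.1 | 80.1 → 86.6 |
| 58/group, screening waived | 80.3 → 83.2 | 80.0 → 86.7 | 80.2 → 92.8 |
| 67/group, lower 40% | 85.8 → 86.7 | 86.0 → 87.8 | 85.2 → 89.8 |
| 67/group, lower 59% | 86.3 → 87.4 | 85.4 → 88.3 | 86.1 → 90.8 |

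Truncation lowers rho to 0.17-0.20, 0.31-0.35 and 0.48-0.53, which is why the low-titre gains are smaller. At rho 0 the adjusted test is about half a point higher (for example 80.2 → 80.6). That is no real gain; it reflects a slightly liberal test, with type I error of 5.1-5.6% against 5.15% exact for chi-squared at 25% response.

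**4. Titres.** At 67 per group, low titres and an assumed 0.5 SD difference, Mann-Whitney power is 80-81%. ANCOVA on log baseline gives 83%, 85-86% and 90-92% at rho 0.3, 0.5 and 0.7. At rho 0 it is 80% v 82%, so about two points come from assuming exactly normal log titres.

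**The case against.** The strongest reply is that nothing here is invalid. Unadjusted tests within randomized strata are sound and the sample size is right for them. That stands. So does the point that the gain is modest for the population the trial mainly targets: at 67 per group it starts from 86%, and for the 65% v 90% row of Table 2 unadjusted power is about 95%, with adjustment adding about 0.5, 1-1.5 and 3 points. The trigger rates rest on definitions the plan does not contain. They show how far the choice of definition matters, not that harm follows. The final analysis plan is also still to come.

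Three stronger readings are tempting, and the documents do not support them.

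- A reader might infer that enrolment anti-RBD is used nowhere. It is a listed secondary time point in the Protocol Summary, section 10.5 reports antibody levels at each time point, and section 7.2.2 uses baseline serology to classify the cellular subset. The gap is only that it is not named as a covariate in a between-group comparison.
- A reader might infer that it is unclear which analysis is primary. No sentence says what happens if the two disagree, but the Protocol Summary and sections 10.2 and 10.5.1 together make chi-squared/Fisher primary and the logistic model an addition.
- A reader might infer an inflated false-positive rate. If both analyses were always run and the better one reported, simulated type I error reaches 7.9% at rho 0.7 without titre restriction. No passage plans that. If the adjusted model were run only when enrolment titre differed at p<0.05, and either significant result counted, it is 5.0-5.2%.

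**Conclusion.** The concern holds as one of precision and pre-specification. The primary and Mann-Whitney comparisons leave out a scheduled baseline measurement, and the one adjusted primary analysis depends on an undefined trigger and an unnamed covariate set. Chance alone could meet that trigger anywhere from 5% of the time (one designated variable at p<0.05) to nearly always (any of 16 above a 0.1 or 0.2 standardized difference). That finding needs no assumption about titre correlation.

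The power forgone does depend on the assumed correlation. At rho 0.3, 0.5 and 0.7 it is about 1-2, 3-4 and 5-7 points from 80% at 58 per group with low titres; about 1, 2-3 and 5 points from 86% at 67 per group; and about 3, 7 and 13 points at 58 per group if screening is waived. These rest on normal log titres, 25% v 50% and, for 67 per group, equal strata. The planned tests are neither biased nor undersized on the plan's own assumptions.

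**What to change.** Before outcome data are seen, in section 10.5 and the final analysis plan:

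- Delete the imbalance condition. Pre-specify, whatever the observed balance, a logistic model in each prior-vaccine stratum with booster and log enrolment anti-RBD. Report a standardized risk difference per stratum, so the result stays on the scale of the 25-point target.
- State in one sentence that chi-squared/Fisher remains primary with this model as the named supportive analysis or, if the sponsor prefers, that the adjusted model governs.
- Use the Study Enrolment sample of Table 1. Section 6.1.3.1 lets study 3604 serology confirm eligibility, so that sample may be missing for some. In that case use the latest pre-booster value or a simple baseline imputation, so that no randomized participant is dropped for want of a baseline value.
- For 1-month anti-RBD and anti-Spike levels, add log-scale ANCOVA on the matching log baseline titre beside the Mann-Whitney test.
- In the exploratory mixed model, use enrolment titre either as a covariate, with only post-booster values as outcomes, or as a response time point, but not both.

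The cost is wording, a little more analysis work and a slightly liberal likelihood-ratio test (about 5.1-5.6%). No new samples are needed.
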